5.3 Identity of Investigational Product

Riociguat is a film-coated, round shaped with 6-mm diameter, immediate-release tablet of pale orange colour. The excipients include lactose, microcrystalline cellulose, crospovidone, magnesium stearate, hypromellose, and sodium lauryl sulfate.

Placebo tablets are identical in appearance to riociguat but do not have the active compound. The excipients include lactose, microcrystalline cellulose, crospovidone, magnesium stearate, hypromellose, and sodium lauryl sulfate.

Study drug will be provided by the drug manufacturer to PPD (designated contract research organisation) for further distribution to sites.

The following drug supplies will be used in the study:

Product	Supplied as
Riociguat	0.5 mg, 1 mg, 1.5 mg, 2 mg and 2.5 mg tablets
Placebo	Matching tablets

5.4 Management of Clinical Supplies

5.4.1 Study Drug Packaging and Storage

Riociguat tablets and matching placebo tablets will be packed in high-density polyethylene bottles à 54 tablets and shipped by PPD Global Clinical Supplies or a third party vendor. Study drug will be packaged and labelled according to applicable local and regulatory requirements. Patients will receive sufficient bottles of randomised dosage for 3 months of treatment which will accommodate the uptitration procedure detailed in section 5.2.

Study drug must be stored in accordance with the manufacturer's instructions. The storage conditions and expiry date are indicated on the label. At the study site, study drug must be stored in a securely locked area and kept at a controlled room temperature not exceeding 25°C (77°F); excursions are permitted from 15°C to 30°C (59°F to 86°F).

The material's schedule will be prepared by an independent PPD statistician and provided to the IWRS and the packaging vendor. At the time of randomisation, the IWRS will assign each patient study drug bottles corresponding to the patient's assigned randomised treatment based on the drug supply inventory that is available at the study site. The bottles

will be identified by a unique bottle number that is separate from the patient randomisation numbers. On Day 1, the investigator will dispense the assigned study drug bottles to the patient as per the patient's randomisation schedule.

5.4.2 Test Article Accountability

The investigator will maintain accurate records of receipt of all test articles, including dates of receipt. In addition, accurate records will be kept regarding when and how much test article is dispensed and used by each patient in the study. Reasons for departure from the expected dispensing regimen must also be recorded. At the completion of the study, to satisfy regulatory requirements regarding drug accountability, all study drugs will be reconciled and retained or destroyed according to applicable regulations.

5.4.3 Other Supplies

Upon site initiation, the PPD Central laboratory will provide initial supplies to the site. The BP measuring device will be provided to each patient.

These supplies include, but are not limited to the following:

- Laboratory manual
- Collection flow chart
- Courier contact sheet
- Specimen collection kits:
 - Prelabelled collection supplies and collection devices (needles, pipettes)
 - Prelabelled requisition form
- Shipping material (AWB# and shipping boxes)
- Study-specific material
 - Urine cups with lid

Further details of the collection of the samples and the supplies used can be found in the laboratory manual and the collection flow chart.

5.5 Overdose Management

An overdose is any dose of study drug given to a patient or taken by a patient that exceeds the dose described in the protocol. Any overdose, with or without associated AEs, must be promptly reported to the PPD Drug Safety Centre. Overdoses without signs or symptoms do not need to be recorded as AEs; in case of any AEs associated with the overdose, these should be reported on relevant AE/SAE sections in the eCRF.

5.5.1 Treatment of Overdose

In cases of overdose, blood pressure should be closely monitored and supportive measures should be provided as appropriate. Based on extensive plasma protein binding, riociguat is not expected to be dialyzable. In case of pronounced hypotension, active cardiovascular support may be required.

5.6 Blinding

The clinical study will be performed in a double-blinded manner. The investigator, study coordinator(s), patients, and the sponsor study team and its representatives will be blinded to the identity of the randomised treatment assignment from the time of randomisation until database lock. Randomisation data will be kept in strict confidence by the statistician who will generate the randomisation schedule, the IWRS provider, and the vendor involved in the study drug labelling. The identity of the treatments will be concealed by the use of study drugs that are all identical in packaging, labelling, schedule of administration, appearance, taste, and odour.

5.6.1 Breaking the Blind

A patient's treatment assignment will not be broken until the end of the study unless medical treatment of the patient depends on knowing the study drug the patient received. In the event that the blind needs to be broken because of a medical emergency, the investigator may unblind an individual patient's treatment allocation. As soon as possible, the investigator should first contact the medical monitor to discuss the medical emergency and the reason for revealing the actual treatment received by that patient. The treatment assignment will be unblinded through IWRS. Reasons for treatment unblinding must be clearly explained and justified in the eCRF. The date on which the code was broken together with the identity of the person responsible must also be documented.

5.7 Treatment Compliance

Patient compliance with study drug will be assessed by the investigator and/or study personnel at each visit using direct questioning and tablet counts. Deviations from the prescribed treatment regimen will be recorded on the source document and the patient's eCRF.

Compliance will be evaluated by calculating the number of tablets taken by the patient divided by the number of tablets expected to be used in the interval between visits.

5.8 Prior and Concomitant Therapy

Patients must be treated with anticoagulants. Drugs with the potential to reduce blood pressure should be used with caution in combination with riociguat, and no drugs named in the exclusion criteria may be administered to patients on riociguat therapy, including nitrates, NO donors, phosphodiesterase inhibitors (including PDE5 inhibitors), ERAs and prostanooids (see exclusion criteria Section 4.1.2).

All concomitant medications taken by the patient during the study, from the date of signature of the informed consent will be recorded in the appropriate section of the eCRF. The minimum requirement is that drug name and the dates of administration are to be recorded. This will include all prescription drugs, herbal products, vitamins, minerals, and over-the-counter medications. Any changes in concomitant medications will also be recorded in the patient's eCRF.

Any concomitant medication deemed necessary for the welfare of the patient during the study may be given at the discretion of the investigator. However, it is the responsibility of the investigator to ensure that details regarding the medication are recorded in full in the eCRF.

6 Study Assessments and Procedures

Before any study procedures are performed, all potential patients will sign an informed consent form (ICF). Patients will have the opportunity to have any questions answered before signing the ICF. The investigator must address all questions raised by the patient. The investigator will also sign the ICF.

Patients will undergo the procedures at time points specified in the Schedule of Events (Table 12-1).

6.1 Demographic and Other Baseline Characteristics

Demographics and other baseline characteristics, including age, body weight (kg), height (cm), waist circumference, race, gender, and medical history will be collected at time points specified in the Schedule of Events (Table 12-1). The data of haemodynamic parameters at screening will be collected from the previous RHC.

6.2 Efficacy Assessments

6.2.1 Pulmonary Vascular Resistance

The resistance offered by the pulmonary circulation is known as the PVR. Pulmonary vascular resistance occurs when the pulmonary artery creates resistance against the blood flowing into it from the right ventricle. The resistance is naturally created by the arrangement of blood vessels in the lungs.

The change in pulmonary resistance from baseline will be measured at the pre-PEA visit (Visit 2) and at the 6-month follow-up visit (Visit 4) after PEA. The PVR value at screening will be collected from the medical history of the patient. The measurements prior to screening will be a prerequisite to confirm participation in study.

6.2.2 Death

The death of the patient irrespective of cause during the study will be reported.

6.2.3 Pulmonary Hypertension–Related Hospitalisation

The incidences of PH-related hospitalisation will be reported during the study for each patient.

6.2.4 Need for Pulmonary Arterial Hypertension–Targeted Medications

The need for PAH-targeted medications will be reported for each patient during the study.

6.2.5 WHO Functional Class

The change in WHO functional class from baseline will be noted at each visit.

WHO functional class is provided in Section 12.2 (Appendix 2).

6.2.6 Need for Other Medications

The need for medications other than PAH-targeted medications will be reported for each patient during the study.

6.2.7 Perioperative Findings

The circulatory arrest time in minutes and surgery-related complications during surgery as mentioned in Table 12-1 will be reported for each patient. Surgery-related complications are defined as the following:

- Bleeding and/or blood loss >1 L in 12 hours
- Airway bleed with need for extracorporeal membrane oxygenation
- Any use of extracorporeal membrane oxygenation for respiratory or haemodynamic support, specified as veno-venous or veno-arterial
- Prolonged ventilation >96 hours
- Need for tracheostomy
- Need for drainage of pericardial effusion
- Neurological complications, ie, stroke, cerebral, subdural bleeding
- Reintubation or noninvasive ventilation for reperfusion response
- Haemoptysis requiring any intervention
- Renal failure requiring dialysis

- Wound infections
- Pneumonia
- Prolonged need for inotropic support (≥ 5 days)

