- When frequency counts are presented, the percentage will be suppressed when the count is zero in order to draw attention to the non-zero counts. A row denoted “Missing” will be included in count tabulations where specified on the shells to account for dropouts and missing values. Percentages will be based on the total number of patients in the respective analysis set unless otherwise specified.
- Unless otherwise specified, statistical tests will be 2-sided and performed using a 5% significance level, leading to 95% (2 sided) confidence intervals (CIs). Modelling techniques will be used in an exploratory sense. No adjustments for multiplicity are made.
- Partial dates will be imputed based on the rules specified in Appendix 13.4.
- All laboratory data will be reported by using the International System of Units.
- Unless otherwise specified, the baseline will be defined as the last valid assessment, including assessments from the unscheduled visit, prior to the study drug administration.
- A Visit 2 assessment is considered as valid only when the assessment is completed within 7 days prior to PEA. For assessments at Visit 4, the nominal visit collected in electronic case report form (eCRF) will be used in the analysis. This rule is applicable to all endpoints derived by the visit.
- By-patient listings will be created for each eCRF module for all screened patients. Patients will be identified in the listings by patient number. If data are to be summarised by visit, the visit name collected on the eCRF page will be used.
- All analyses will be conducted using SAS® software Version 9.3 or later (SAS Institute Inc, Cary, North Carolina).

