8.2.3.2. Surgery-related Complications

Surgery-related complications at Visit 2 from the perioperative findings will be tabulated by treatment group in a descriptive way for the PEA set, presenting the number and percentage of patients for each symptom. The Fisher exact test will be utilised to test the proportion difference along with the Clopper-Pearson exact CI.

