13.3. Surgery-related complications

Surgery-related complications are defined as the following:

- Bleeding and/or blood loss >1 L in 12 hours
- Airway bleed with need for extracorporeal membrane oxygenation
- Any use of extracorporeal membrane oxygenation for respiratory or haemodynamic support, specified as veno-venous or veno-arterial
- Prolonged ventilation >96 hours
- Need for tracheostomy
- Need for drainage of pericardial effusion
- Neurological complications, ie, stroke, cerebral, subdural bleeding
- Reintubation or noninvasive ventilation for reperfusion response
- Haemoptysis requiring any intervention
- Renal failure requiring dialysis
- Wound infections
- Pneumonia
- Prolonged need for inotropic support (≥ 5 days)

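### Two of the 13 surgery-related complications can be met only by patients who survive to a time threshold, and the SAP has no rule for earlier death, so these two rows slightly favour an arm with more early deaths

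*Protocol*

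**What the plan says.** Protocol 6.2.7 defines the surgery-related complications, and SAP 13.3 repeats the list. There are 13 items and death is not one of them. Two items carry an explicit duration: "Prolonged ventilation >96 hours" and "Prolonged need for inotropic support", the latter with a limit of 5 days or more.

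SAP 8.2.3.2 has the items "tabulated by treatment group in a descriptive way for the PEA set, presenting the number and percentage of patients for each symptom". It then adds inference: "The Fisher exact test will be utilised to test the proportion difference along with the Clopper-Pearson exact CI". Protocol 7.8.2 planned only the descriptive table for this endpoint.

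The denominator comes from SAP section 4 (General Statistical Considerations): "Percentages will be based on the total number of patients in the respective analysis set unless otherwise specified". Under SAP 4.3.2 the PEA set is every treated patient who is operated on, so it includes those who die during or soon after surgery. SAP 8.2.3.2 specifies no other denominator and does not mention death.

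Death is analysed elsewhere in the same set. SAP 8.2.5 covers all-cause death, with counts and Kaplan-Meier. SAP 8.3 covers in-hospital mortality, with a difference between arms and an interval. Neither output is linked to the complication table.

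**The concern.** A patient who dies on day 2, ventilated and on inotropes, has had one of the worst possible courses after surgery. By the definitions that patient can have neither more than 96 hours of ventilation nor 5 days of inotropes. The planned table therefore scores the patient as free of both.

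If early deaths differ between the arms, the two rows and their Fisher tests lean towards the arm with more of them. The documents give a reason to consider such a difference. Protocol 1.1 says operative risk is higher with high preoperative pulmonary vascular resistance, and Protocol 1.5 says riociguat may lower that risk. If riociguat prevents early deaths, these rows count slightly against it; if it causes them, the rows flatter it.

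The complications are a secondary endpoint and bear on the stated objective about safety and efficacy aspects during the operation.

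**Working it through.** **Inputs**

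- Operated patients per arm, n = 40. This is half of the 80 completers targeted in Protocol 4.3.3, and its use as the number operated is an assumption.
- Perioperative mortality 4.7% (Protocol 1.1, SAP section 1). It covers all perioperative deaths, not only those before 96 hours or day 5.
- Risk p of the item among patients who live to the threshold. The documents give no complication rates, so there is no planned figure to reproduce. I assume p = 20% in both arms, with 10% and 30% as a range.
- Number d of deaths before the threshold, also assumed.

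**Expected deaths.** 40 × 0.047 = 1.88 per arm, or 44 × 0.047 = 2.07 if all randomised patients are operated on. Not all of these would fall before the threshold. At 4.7%, four or more perioperative deaths among 40 patients have binomial probability of about 0.12.

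**Rate as planned.** None of the d patients can be in the numerator, and all are in the denominator:

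rate = p(n − d)/n

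With equal n and p, the difference between arms is −p(d₁ − d₂)/n. This is zero when early deaths are equal.

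| p | d = 1 vs 0 | Difference | d = 4 vs 1 | Difference |
|---|---|---|---|---|
| 10% | 9.75% vs 10.0% | −0.25 points | 9.0% vs 9.75% | −0.75 points |
| 20% | 19.5% vs 20.0% | −0.5 points | 18.0% vs 19.5% | −1.5 points |
| 30% | 29.25% vs 30.0% | −0.75 points | 27.0% vs 29.25% | −2.25 points |

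A negative difference means that the arm with more early deaths looks better. At p = 20%, 1.5 points is 0.6 of a patient in 40.

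**Rate with early death counted as an event.**

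rate = [p(n − d) + d]/n

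For p = 20% and d = 4 vs 1: (0.2 × 36 + 4)/40 = 28.0% against (0.2 × 39 + 1)/40 = 22.0%, a difference of +6.0 points. For p = 10% it is +6.75 points and for p = 30% it is +5.25 points.

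**Effect on the test.** The whole-patient counts nearest to the 20% case are 7/40 vs 8/40 as planned (Fisher p = 1.0) and 11/40 vs 9/40 with early deaths counted (p = 0.80). Neither is near the 5% level.

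**Items without a duration.** Bleeding, extracorporeal support and stroke can occur before an early death. If a share q of those who die early had already met such an item, the rate is [p(n − d) + qd]/n, which falls below p only when q < p. With n = 44, d = 6 and p = 20%, the rate is 17.3% for q = 0, 20.0% for q = 20% and 24.1% for q = 50%. More deaths can therefore raise these rows. Pneumonia, wound infection, tracheostomy and dialysis carry no stated duration, so an effect there is possible but does not follow from the definitions.

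**The case against.** The strongest case for leaving the table alone has four parts.

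- **Deaths are not hidden.** All-cause death and in-hospital mortality are both tabulated in the PEA set, and death is also in the six-month composite. A reader can see an imbalance. This stands, and it makes a further row for in-hospital deaths optional. But neither output says how many died before 96 hours or day 5, and neither enters the two tested rows.
- **The distortion is small.** This stands. The 4 vs 1 case is already an unfavourable one, since it puts all those deaths before the threshold. Protocol section 7 also declares all analyses exploratory, and the sample size is not based on power.
- **The change of sign is built in.** A reader might infer from −1.5 and +6.0 points that the planned analysis gets the direction of the treatment effect wrong. That does not follow. With equal p and three more early deaths in one arm, the two differences are −p × 7.5 and +(1 − p) × 7.5 points, where 7.5 is 3/40, so they have opposite signs for every p between 0 and 1. The second figure is mostly the mortality difference and answers a different question.
- **Counting death mixes two outcomes.** This is also fair, and it is why the item-only counts should stay visible.

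A reader might also infer that more operative deaths lower an arm's complication rates across the whole list. The documents do not support that: only two of the 13 items require survival to a stated time.

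**Conclusion.** The gap is real for two rows of the complication table: ventilation beyond 96 hours and inotropic support for 5 days or more. By definition and denominator, death before the threshold is scored as absence of the item, and nothing in the protocol or SAP repairs this. The direction is known: the rows favour the arm with more early deaths.

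The size is about 0.5 points for a difference of one early death and 1.5 points for 4 vs 1, with a range of 0.75 to 2.25 points for the latter when the risk is 10% to 30%. This rests on 40 operated patients per arm, equal risk among those who reach the threshold, and assumed early deaths. No conclusion of the trial is shown to change. This is a low-severity point and a cheap improvement.

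**What to change.** In SAP 8.2.3.2, for the two duration-defined items only:

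1. Add a row for the item or death before the threshold while still ventilated (first item) or still on inotropes (second item).
2. State that death in theatre or before intensive care admission counts as an event in both rows. This has to be explicit because Protocol 6.2.16 starts the ventilation clock at the intensive care stay, which such a patient never has.
3. Apply the Fisher test and interval to the added row.
4. Beside it, keep the item-only count and show the number who died before the threshold.

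A separate row for in-hospital deaths is optional, since SAP 8.3 already plans that output.

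The cost is SAP wording and a derived flag for each item, with no new visits or patients. Dates of surgery and death and the end of ventilation are needed for other planned outputs. The inotrope flag depends on the administration dates that Protocol 5.8 requires for concomitant medication, so their completeness should be checked. The drawback is that the two added rows combine death with a complication, which the counts in step 4 keep transparent.

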6.2.8 Surgical Evaluation of Specimen

The difficulty to withdraw the obstructive material will be measured as specified in Section 6.2.8.1, Section 6.2.8.2, and Section 6.2.8.3 scores as follows:

6.2.8.1 Ease of Dissection

The ease of dissection will be measured as a score of 1 to 3 with scores easier than normal (1), normal (2), and more difficult than normal (3).

6.2.8.2 Completeness of Disease Clearance

The completeness of disease clearance will be measured as a score of 1 to 3 with scores better than expected (1), as expected (2), and worse than expected (3).

6.2.8.3 Evaluation of Clot and Vessel Wall

Both clot and vessel wall will be measured as a score of 1 to 3 with the following scores: more solid than usual (1), normal (2), more friable than usual (3).

6.2.9 Withdrawal During Randomised Treatment Phase

The withdrawal of the patient during the treatment phase after randomisation along with the reason for withdrawal will be reported.

6.2.10 Plasma Pro-Brain Natriuretic Peptide Concentration

The plasma NT-proBNP concentration will be measured at baseline, pre-PEA, and at the 6-month follow-up visit after PEA. The change in NT-proBNP concentration from baseline at the pre-PEA visit (Visit 2) and at the 6-month follow-up visit (Visit 4) will be reported.

6.2.11 Cardiac Index

Cardiac index is a cardiodynamic parameter measured by the amount of blood ejected by left ventricle into the systemic circulation in 1 minute divided by body surface area. The unit of measurement is litres per minute per square metre (L/min/m²). The cardiac index will be measured at the pre-PEA visit (Visit 2) and at the 6-month follow-up visit after PEA (Visit 4). The cardiac index value at screening will be collected from the medical history of the patient. The measurement prior to screening will be a prerequisite to confirm participation in study. The method of measurement of cardiac output (thermodilution or Fick method) should be consistent for each patient. If thermodilution method is available, this should be recorded.

6.2.12 Mean Right Atrial Pressure

The mRAP will be measured at the pre-PEA visit (Visit 2) and at the 6-month follow-up visit after PEA (Visit 4). The mRAP value at screening will be collected from the medical history of the patient.

